#### **Specific measures to consider after epinephrine injections, where appropriate**

- (j) Consider epinephrine infusion.
- (k) Consider H1 and H2 antihistamines
- (l) Consider nebulized  $\beta$ 2 agonist (eg, albuterol [salbutamol]) for bronchospasm resistant to epinephrine
- (m) Consider systemic corticosteroids
- (n) Consider vasopressor (eg, dopamine)
- (o) Consider glucagon for patient taking a  $\beta$  -blocker
- (p) Consider atropine for symptomatic bradycardia
- (q) Consider transportation to an emergency department or an intensive care facility
- (r) For cardiopulmonary arrest during anaphylaxis, high-dose epinephrine and prolonged resuscitation efforts are encouraged, if necessary

Adapted from: Kemp SF, Lockey RF, Simons FE; World Allergy Organization ad hoc Committee on Epinephrine in Anaphylaxis. Epinephrine: the drug of choice for anaphylaxis. A statement of the World Allergy Organization. Allergy 2008;63(8):1061-70.

## Appendix J: Adrenal Crisis Guidelines

### **Management of Acute Adrenal Insufficiency Secondary to Glucocorticoid Withdrawal**

National or local guidelines for the management of acute adrenal insufficiency (adrenal crisis), where they exist, should be followed. The following guidelines have been adapted from the guidelines of the Society for Endocrinology. They are intended for guidance subject to clinical judgement only.

The possibility of acute adrenal insufficiency should be considered in any acutely unwell patient undergoing withdrawal of chronic systemic corticosteroid treatment.

#### **Recognition**

- Clinical signs and symptoms
  - Fatigue, lack of energy, weight loss
  - Low blood pressure, postural dizziness and hypotension ( $\geq 20$  mmHg drop in systolic BP from supine to standing position), dizziness, collapse, and in severe cases hypovolaemic shock
  - Abdominal pain, tenderness and guarding, nausea, vomiting
  - Fever
  - Confusion, somnolence, in severe cases delirium or coma
  - Back and leg cramps/spasms may be reported
- Lab findings:
  - Hyponatraemia
  - Pre-renal failure (increased serum creatinine due to hypovolaemia)
  - Normochromic anaemia, sometimes also lymphocytosis and eosinophilia
  - Hypoglycaemia

#### **Management**

- **Hydrocortisone** (immediate bolus injection of 100 mg hydrocortisone i.v. or i.m. followed by continuous intravenous infusion of 200 mg of hydrocortisone per 24 hours (alternatively 50 mg of hydrocortisone per intravenous or intramuscular injection every 6 hours))
- **Rehydrate** with intravenous 0.9% sodium chloride in hypotensive patients. The rate and total volume of infusate must be decided on an individual patient basis with continuous monitoring for fluid overload. Correction of hyponatraemia must be according to relevant local guidelines

- Consider any other potential precipitating factors (in addition to corticosteroid withdrawal), eg, infection; investigate and treat as appropriate

Contact an endocrinologist at an early stage to advise on ongoing management.

## Appendix K: PONENTE Long Term Follow Up Substudy

### 1. PONENTE Long Term Follow Up Substudy Background and Rationale

The PONENTE study assesses an algorithm for OCS reduction that also defines when OCS reduction should be interrupted (i.e. after 2 exacerbations, or after two laboratory tests showing complete AI within a 3-month period). Once the OCS dose has been completely reduced or the lowest OCS dose achieved based on the OCS reduction treatment algorithm, patients enter a maintenance phase where no further reductions in OCS dose are allowed. After completing the 6-month OCS maintenance phase, patients who couldn't completely reduce OCS may have been well-controlled on the lowest OCS dose achieved during the OCS reduction phase or may have recovered from AI, and, therefore, healthcare providers may decide to further reduce OCS or other background asthma medication, which is in line with the GINA report on severe asthma management (i.e. first reducing OCS and then, reducing ICS dose as tolerated according to clinical assessment) ([GINA 2020](#)).

According to the GINA report, asthma therapy should be periodically reviewed to assess patient's response to therapy. For patients who have had a good response to biologic therapy, the treating physician should consider not only the reduction or elimination of maintenance OCS, but also reducing the ICS dose from high to medium dose (GINA 2020). GINA describes this guidance as "consensus advice" recognizing that no data are available to guide this clinical decision.

However, it is anticipated that in the future healthcare providers are likely to reduce the ICS dose significantly or completely at the behest of patients whose asthma becomes well-controlled after the addition of biologic therapy.

This long term follow up substudy aims to observe changes in the OCS dose and other background asthma therapy, and to assess the amount of recovery from AI, in a real-world setting as well as assessment of glucocorticoid toxicity by means of GTI.

### 2. PONENTE Long Term Follow Up Substudy Design

After completion of the EOT visit procedures, eligible patients (See Appendix K – Section [4](#) and [5](#)) may consent to a long term follow up visit 12 to 18 months after completion of the main PONENTE study. Accordingly, the long term follow up visit can occur in a range of 12 to 18 months after an eligible patient completes the EOT visit such that the last visit of the PONENTE Long Term Follow Up will take place 1-year after the last patient completes the EOT of the main PONENTE study.

Patients will be treated according to healthcare provider discretion and therefore no IP (i.e. Benralizumab) will be provided by the sponsor. Between the EOT visit of the main PONENTE study and the Long Term Follow Up visit, any changes in the maintenance asthma regimen are allowed, including further reductions of OCS as recommended in the GINA report ([GINA 2020](#)).

## **2.1 Consent:**

Written consent must be obtained at any time from the EOT visit to prior to the Long Term Follow Up visit. Patients will complete the 4-week follow-up visit after EOT, regardless of whether they enrol in the long term follow up substudy, as this is the last visit of the PONENTE study.

Patients who have already completed the EOT visit or the follow-up visit before the start of the PONENTE Long Term Follow Up may be contacted after EOT for participation. In this case, all assessments previously captured during the EOT visit will be included in the analysis of the PONENTE Long Term Follow Up.

Enrolment into the long term follow up substudy will remain open until the last PONENTE patient has completed the EOT visit.

## **2.2 Long Term Follow Up Visit:**

At the Long Term Follow Up visit, the patient will undergo an on-site visit for assessment of daily OCS dose, concomitant medications (including changes in background asthma regimen), asthma exacerbations, laboratory assessments, vital signs, and items for the GTI assessments. Additionally, patients who had Complete or Partial AI at the end of the OCS maintenance phase (EOT visit) of the primary PONENTE study, will undergo morning cortisol testing. Patients with indeterminate results from the morning cortisol test at the Long Term Follow Up visit will return on-site to conduct ACTH stimulation test within a week after the Long Term Follow Up visit.

## **2.3 Assessment and collection of asthma exacerbations:**

Asthma exacerbations will be defined per Section 5.2.2. The Investigator will assess exacerbations at the PONENTE Long Term Follow Up, and if applicable, at any other time when made aware by the patient (Table 8). The Investigator must justify the decision for defining an event of worsening asthma as an exacerbation, and document this justification, including symptoms, in the source documents and the eCRF.

## **2.4 Safety reporting:**

Any event that occurs from the time period between the main PONENTE study follow up visit and the patient signing the ICF will be captured as part of the medical history for the PONENTE Long Term Follow Up. After PONENTE Long Term Follow Up informed consent up until the Long Term Follow Up visit, any events will be captured as AEs/SAEs. Any AE/SAE that are unresolved at the Long Term Follow Up visit will be followed-up by the Investigator as long as medically necessary but will not be captured in the eCRF. Causality will be confirmed by the investigator per Section 6.3.4. Adverse events based on signs and symptoms, or based on examinations and tests, will be reported per Sections 6.3.5 and 6.3.6, respectively.

Any spontaneous reports of AE/SAE related to any drug products other than benralizumab will not be captured in the eCRF but will be reported as spontaneous reports to the drug

manufacturer (e.g. to AstraZeneca or other manufacturer) and/or local regulatory agencies as required by local regulations.

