## 6. Study Plan and timing of procedures

**Table 8 PONENTE Long Term Follow Up Substudy – Study plan: Enrolment to End of Study**

Assessment/Activity	Protocol section	Enrollment	Long Term Follow Up Period	Withdrawal	Unscheduled Visit
		PONENTE Long Term Follow Up Enrolment (after EOT procedures) a	PONENTE Long Term Follow Up Visit		
Written Informed consent for long term follow up substudy b	Appendix K: 2.1	X			
Medical History		X			
Review EOT Visit Assessments	Table 1	X			
Brief physical examination	5.2.5.2	N/A		X	X
Vital signs	5.2.6	N/A	X	X	X
Weight	5.3.1	N/A	X	X	
Serum chemistry	5.2.4	N/A	X	X	
Hematology	5.2.4	N/A	X	X	
Morning Cortisol testing c	5.2.4	N/A	X	X	
Glucocorticoid toxicity index	5.2.1.1	N/A	X	X	
Assessment of asthma exacerbations	5.2.2/5.2.3	N/A	X	X	X
Adverse events	6.1	N/A	X	X	X
Concomitant medication	7.8 / Appendix K: 7	N/A	X	X	X
OCS and asthma medications	Appendix K: 7	N/A	X	X	X

- a. Enrolment for the PONENTE Long Term Follow Up substudy can occur any time after all PONENTE EOT procedures are completed. Patients who have already completed EOT prior to the start of the PONENTE Long Term Follow Up substudy may be contacted for participation at any time up to 18 months after the EOT visit. Assessments labeled N/A are not applicable because they will be collected as a part of the PONENTE EOT visit.
- b. ICF for the PONENTE Long Term Follow Up substudy must be obtained any time from EOT of the main PONENTE study and prior to any activities of the PONENTE Long Term Follow Up visit
- c. Patients who have Complete AI or Partial AI at the end of the primary PONENTE study will undergo a morning cortisol test at the Long Term Follow Up visit. Patients with indeterminate results will return to the site within a week after the Long Term Follow Up visit to conduct an ACTH stimulation test.

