## **7. Concomitant medication and other treatments**

The PONENTE Long Term Follow Up is observational only. There are no sponsor-provided investigational products, restrictions related to concomitant medications other than those detailed in Section 3.5, or restrictions on concurrent disease. Restrictions described in Section 7.8 do not apply in the PONENTE Long Term Follow Up.

Additionally, from the EOT visit of the main PONENTE study to the Long Term Follow Up visit, any changes in the maintenance asthma regimen are allowed, including reductions of maintenance OCS therapy as recommended in the GINA report.

Due to potential interactions with morning cortisol and ACTH stimulation testing, the restrictions on concomitant medications detailed in Section 3.5 remain in place for the PONENTE Long Term Follow Up substudy.

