### **Analysis of safety outcomes**

The number and percentage of patients with complete AI at the Long Term Follow Up visit will be presented for the long term follow up analysis set, biologic analysis set and Benralizumab analysis set. A logistic regression model will be developed to identify factors potentially predictive of long-term adrenal insufficiency. Complete AI status at the Long Term Follow Up visit will be the dichotomous response variable with demographic, respiratory and metabolic baseline characteristics as explanatory variables. Full details will be provided in the SAP.

Spaghetti plots will be produced for patients in the long term follow up analysis set, biologic analysis set and Benralizumab analysis set with partial AI throughout the OCS reduction phase of the main PONENTE study, showing cortisol levels over time until the Long Term Follow Up visit.

The incidence of AEs and SAEs will be summarized over the PONENTE Long Term Follow Up substudy for comparison with incidence rates during the PONENTE main study. Summaries of laboratory parameters and vital signs may be provided, including absolute values and changes over time. Full details will be provided in the SAP.

The annualized rate of asthma exacerbations during the PONENTE Long Term Follow Up substudy will be summarized using mean, 95% CI and dispersion based on the negative binomial distribution, for the long term follow up analysis set, biologic analysis set and Benralizumab analysis set. This will be repeated for exacerbations resulting in hospitalization or an ER visit. Rates will be compared with those recorded during the PONENTE main study. The number and percentage of patients remaining exacerbation-free during the PONENTE Long Term Follow Up substudy will be presented.

Glucocorticoid toxicity index will be summarized over time from the start of the PONENTE main study to the end of the PONENTE Long Term Follow Up substudy, for the long term follow up analysis set, biologic analysis set and Benralizumab analysis set. Statistical correlation between GTI and daily OCS dose will be explored.

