## **9. Study timetable and end-of-study**

Enrolment for the PONENTE Long Term Follow Up substudy will be closed once the final PONENTE patient completes the EOT visit. For patients who participate in the PONENTE Long Term Follow Up substudy, the final study visit will be the Long Term Follow Up visit except for patients with indeterminate morning cortisol results at this visit who will return within 1 week after Long Term Follow Up visit to conduct the ACTH stimulation test.

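### Appendix K 2.4 closes substudy adverse-event capture at the Long Term Follow Up visit, up to a week before the ACTH test that some patients must still undergo, so non-serious events in that interval are outside the stated window

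*Protocol*

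**What the plan says.** Three parts of Protocol Appendix K bear on this point.

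- **Safety window (2.4).** Events before substudy consent, back to the main-study follow-up visit, are medical history. From consent onward: "After PONENTE Long Term Follow Up informed consent up until the Long Term Follow Up visit, any events will be captured as AEs/SAEs". Events "unresolved at the Long Term Follow Up visit will be followed-up by the Investigator as long as medically necessary but will not be captured", meaning that they are not entered into the eCRF. A second paragraph sends spontaneous reports concerning products other than benralizumab to the manufacturer or local regulator and keeps them out of the eCRF.
- **ACTH test (2.2, and Table 8 footnote c).** Patients with complete or partial AI at EOT have a morning cortisol test at the Long Term Follow Up visit. Those with an indeterminate result "will return on-site to conduct ACTH stimulation test within a week after the Long Term Follow Up visit". Footnote c agrees: "Patients with indeterminate results will return to the site within a week after the Long Term Follow Up visit". Main-text Section 5.2.1.2 gives the intravenous route.
- **End of substudy (9).** For participants, "the final study visit will be the Long Term Follow Up visit except for patients with indeterminate morning cortisol results at this visit"; those patients finish at the ACTH return.

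Section 6.3.1 of the main text refers to Appendix K for substudy safety reporting and sets no window of its own for it. In Table 8 the adverse-event row is marked for the Long Term Follow Up visit, for withdrawal and for unscheduled visits. There is no column for the ACTH return.

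**The concern.** A safety window normally runs at least to the last procedure that the protocol requires. Here the stated window stops first. The substudy is observational and, in the words of Appendix K 7, "There are no sponsor-provided investigational products", so the ACTH injection is the only drug administration that its protocol requires. It goes to patients who had complete or partial AI at EOT. The medication-withholding rules of Section 3.5 apply before it, so that preparation can also fall after the window closes.

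At stake is the recording of non-serious events around this test. Adverse events are a listed substudy safety outcome, and Appendix K 8.5 plans that their incidence "will be summarized over the PONENTE Long Term Follow Up substudy for comparison with incidence rates during the PONENTE main study".

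**Working it through.** The plan states no figure to reproduce. The check is a comparison of dates.

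**Substudy timeline**, with day 0 the Long Term Follow Up visit:
- Capture ends: day 0 (Appendix K 2.4).
- ACTH test, where needed: day 0 to day 7 (Appendix K 2.2, Table 8 footnote c, Appendix K 9).
- Uncovered interval = day of test − day 0 = 0 to 7 days.

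The return cannot easily be read as part of the Long Term Follow Up visit, because Appendix K 9 treats it as an exception to that visit being the last one. Events after consent and before day 0 are inside the window. The gap runs only from day 0 through the test.

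**Who is affected.** Both conditions must hold: complete or partial AI at EOT, and an indeterminate cortisol at the Long Term Follow Up visit. The documents give no count or expected proportion for either.

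**Main study for contrast**, in weeks after the last benralizumab dose:
- EOT: week 8 (Section 1.4.4).
- Final morning cortisol, 1 to 2 weeks earlier: 8 − 2 = 6 to 8 − 1 = 7.
- ACTH test within about 1 week of that (Section 1.4.3): weeks 6 to 8.
- Capture closes: week 12 (Section 6.3.1).
- Margin: 12 − 8 = 4 to 12 − 6 = 6 weeks.
- With EOT 7 days late and follow-up 7 days early: test by week 9, capture closes at week 11, margin at least 2 weeks.

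So in the main study the last planned ACTH test lies inside the window with weeks to spare; in the substudy it lies at or beyond the edge.

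**Size relative to the covered window**, if consent is given at EOT:
- Visit at 12 months: 7 / 365 = 1.9%.
- Visit at 18 months: 7 / 548 = 1.3%.

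**Serious events.** Section 6.4 requires every serious event in the course of the study to be reported, whether or not it is linked to a procedure. Section 9.3 counts a patient as complete only after the last scheduled contact, which here is the ACTH return. Section 6.3.4 implies causality where a serious event could be associated with a study procedure. Serious events at the test therefore have a route, and for them Appendix K 2.4 is only worded inconsistently.

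**The case against.** The case for leaving the text alone has five parts.

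- **Unscheduled visits.** Table 8 collects adverse events there, and a site might log the ACTH return that way. Table 1 footnote q does so for unscheduled blood draws in the main study. This stands as a partial safeguard. But nothing classifies the ACTH return as unscheduled, the cortisol row of Table 8 is not marked in that column, and Appendix K 2.4 would still end earlier.
- **Non-benralizumab products.** The ACTH stimulant is one, so a spontaneously reported reaction to it already has a route outside the eCRF. This stands, and it shapes the remedy: moving the end date alone might not bring such reactions into the eCRF. The position is unclear, because Appendix K 2.4 also invokes Section 6.3.5, under which volunteered, solicited and observed events are all recorded.
- **The stated objective.** The substudy safety objective in Appendix K 3 also runs to the long-term follow-up visit. However, the AI-shift outcome has the same end point and still depends on the later ACTH result in these patients, so that wording does not show that the return was meant to be excluded.
- **The unresolved-event rule.** Not recording the later course of open events is also the main-study rule (Section 6.3.2). This stands: the rule is ordinary, and only its reference date is at issue.
- **Small yield.** Section 6.3.6 already keeps most AI signs and symptoms from counting as adverse events. This stands too.

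A reader might infer three stronger things that the documents do not support. The first is that serious events at the ACTH test would be lost; Sections 6.4, 9.3 and 6.3.4 say otherwise. The second is that the planned comparison of incidence with the main study is materially distorted. The gap is at most 7 days in a subset, and the analysis detail is left to a separate substudy SAP that is not among the documents, so no such effect can be shown. The third concerns late consent. Appendix K 2.1 says "Written consent must be obtained at any time from the EOT visit to prior to the Long Term Follow Up visit", so the covered window can be shorter than the gap if consent comes less than a week before the visit. That follows from the consent rule and would hold without any ACTH test, so it adds nothing to this point.

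**Conclusion.** The point holds as a small correction to the safety window. As written, non-serious adverse events after the Long Term Follow Up visit and through the ACTH test, 0 to 7 days, fall outside the capture period for patients with complete or partial AI at EOT and an indeterminate cortisol at that visit. The exception is a site that chooses to log the return as unscheduled.

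This rests on reading the Long Term Follow Up visit and the ACTH return as separate contacts, as Appendix K 9 does, and on Section 6.3.1 leaving the substudy window to Appendix K. The size of the subset is unknown. Reporting of serious events is intact and no main-study endpoint is touched. The change is worth making because it costs almost nothing, not because the expected loss is large.

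**What to change.** Make three wording changes.

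1. In Appendix K 2.4, end both the capture period and the unresolved-event rule at the later of the Long Term Follow Up visit and completion of the ACTH test visit.
2. In the same section, state that adverse events at or related to the ACTH test are recorded in the eCRF, notwithstanding the paragraph on spontaneous reports for products other than benralizumab.
3. In Table 8 footnote c, note that adverse events are collected at the ACTH return.

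The cost is an edit to one section and one footnote, plus minor data entry at an on-site contact that already takes place. No additional visit, sample or analysis is needed.

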#### 6.3.4 Causality collection

The Investigator will assess the causal relationship between the study drug and each AE, and answer 'yes' or 'no' to the question, 'Do you consider that there is a reasonable possibility that the event may have been caused by the study drug?'

For SAEs, the causal relationship will also be assessed for other medication and study procedures. Note that for SAEs that could be associated with any study procedure, the causal relationship is implied as 'yes'.

A guide to the interpretation of the causality question is found in Appendix [A](#) to the Clinical Study Protocol.

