### **6.3.5 Adverse events based on signs and symptoms**

All AEs spontaneously reported by the patient, reported in response to the open question from the study site staff, '*Have you had any health problems since the previous visit/you were last asked?*', or revealed by observation will be collected and recorded in the eCRF. When collecting AEs, the recording of diagnoses is preferred (when possible) to recording a list of signs and symptoms. However, if a diagnosis is known and there are other signs or symptoms that are not generally part of the diagnosis, the diagnosis and each sign or symptom will be recorded separately.

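### Appendix K 2.4 gives conflicting rules on whether adverse events attributed to products other than benralizumab enter the substudy eCRF, which leaves the planned AE comparison with the main study open to under-counting

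*Protocol*

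**What the plan says.** Protocol Appendix K 2.4 sets the substudy's safety reporting in two paragraphs.

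The first gives a general rule: "After PONENTE Long Term Follow Up informed consent up until the Long Term Follow Up visit, any events will be captured as AEs/SAEs". It then brings in the main-study procedures: "Causality will be confirmed by the investigator per Section 6.3.4", and "Adverse events based on signs and symptoms, or based on examinations and tests, will be reported per Sections 6.3.5 and 6.3.6, respectively". Section 6.3.5 covers "All AEs spontaneously reported by the patient, reported in response to the open question from the study site staff" as well as events found by observation, and directs all of them to the eCRF. Section 6.3.4 adds: "For SAEs, the causal relationship will also be assessed for other medication and study procedures".

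The second paragraph gives a specific rule: "Any spontaneous reports of AE/SAE related to any drug products other than benralizumab will not be captured in the eCRF". Those reports go instead to the manufacturer, to local regulators, or to both.

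In the main study, Section 6.3.3 has every AE recorded in the eCRF, with no condition on the suspected drug. Appendix K 8.5 (Analysis of safety outcomes) summarizes substudy AE and SAE incidence "for comparison with incidence rates during the PONENTE main study".

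**The concern.** The substudy supplies no investigational product and allows any change of maintenance asthma regimen (Appendix K 2). Appendix K 8.3 defines an analysis set for exposure to any asthma biologic. Events attributed to something other than benralizumab are therefore to be expected.

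For such an event raised by the patient, one paragraph says record it and the next says do not. Section 6.3.1 sends sites to Appendix K for substudy safety reporting, so a site could reasonably treat the more specific second paragraph as the one that prevails. Other sites could follow the first.

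An event kept out of the eCRF leaves no trace there, so the analysis could neither detect nor correct the omission. A lower AE incidence in the substudy than in the main study might then reflect the recording rule and not the patients' experience.

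**Working it through.** The plan gives no figure to reproduce. The check is a reconciliation of text, followed by an illustration of direction.

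**1. Is there a real conflict?** Take an AE that a consented patient reports unprompted and that the investigator attributes to a product other than benralizumab.

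| Source | What happens to this event |
|---|---|
| Appendix K 2.4, first paragraph | Captured as an AE/SAE |
| Section 6.3.5, applied by Appendix K 2.4 | Recorded in the eCRF, because patient-reported events are named there |
| Section 6.3.4, applied by Appendix K 2.4 | If serious, causality is also judged against other medication, which presupposes that the event is on record |
| Appendix K Table 8 | AEs collected at the follow-up, withdrawal and unscheduled visits under Section 6.1, whose definition does not depend on drug relationship |
| Appendix K 2.4, second paragraph | Not captured in the eCRF if it counts as a *spontaneous report* |

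Section 6.3.5 uses spontaneous reporting by the patient as a route into the eCRF. Appendix K 2.4 uses spontaneous reports as a ground for staying out of it. Appendix K does not say how the two differ, so the conflict stands for this event.

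**2. Does the main study have the same filter?** No. Section 6.3.3 records all AEs. Section 6.4 requires SAEs to be reported and recorded whether or not they are thought related to study drug. Sections 6.3.6 and 6.3.8 restrict when signs of AI and asthma symptoms count as AEs, but those limits do not turn on the suspected drug.

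**3. Which way does the comparison move?** Let the true AE rate be λ in both periods, and let s be the share of substudy AEs left out under the second paragraph. The documents give no value for s.

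- Recorded main-study rate: λ
- Recorded substudy rate: λ(1 − s)
- Recorded rate ratio, substudy to main study: 1 − s

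| Assumed s | Rate ratio with no true change |
|---|---|
| 0% (the first paragraph governs everywhere) | 1.00 |
| 5% | 0.95 |
| 10% | 0.90 |
| 20% | 0.80 |

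For the proportion of patients with at least one AE, assume Poisson counts and a true proportion p. The recorded proportion is then 1 − (1 − p)^(1 − s). With an assumed p of 50%, s = 0 gives 50.0% and s = 10% gives 1 − 0.5^0.9 = 46.4%.

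These values of s and p are illustrations. The direction is fixed, since omission can only lower the substudy count. The size is not.

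**The case against.** The best defence is that the second paragraph is only a routing rule. In pharmacovigilance usage, a spontaneous report can mean an unsolicited report made outside a study's own AE collection. On that reading the first paragraph, Sections 6.3.4 and 6.3.5, and Table 8 all require events elicited at the visit to be recorded, and nothing is lost. This reading is possible and may be what was intended. But the text does not state it, and Section 6.3.5 uses the same word for events that are recorded.

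Three further points have weight:

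- For non-serious AEs, causality is recorded only against study drug (Sections 6.3.3 and 6.3.4). The documents give no routine basis for classing them as related to another product. This makes the size less predictable and may make it small.
- The comparison is descriptive, with no hypothesis tested (Appendix K 8.5). Its comparability is already limited, because events between the main-study follow-up visit and substudy consent become medical history (Appendix K 2.4). AE observation time therefore depends on the consent date.
- The substudy has its own SAP, which is not among the documents and may narrow the comparison.

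A reader might infer more than the text supports. One inference is that every AE related to another drug is excluded. The rule covers spontaneous reports only, and the neighbouring provisions point towards recording. A second is that OCS-related harm disappears from the substudy. It is also measured through the GTI, cortisol and ACTH testing, laboratory parameters and vital signs. A third is that the Benralizumab and Biologic analysis sets would be biased against each other. Only the general tabulation sentence in Appendix K 8.5 bears on this. The AE sentence names no analysis sets, and no between-set AE contrast is defined.

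**Conclusion.** The concern holds as a contradiction in the recording rule, with a consequence that depends on how sites resolve it. Where a site applies the second paragraph, AEs attributed to OCS, another biologic or any other product are missing from the substudy eCRF, and the AE/SAE comparison with the main study is biased towards lower substudy incidence.

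The size cannot be determined from the documents. It is zero if the first paragraph governs at every site; otherwise the rate ratio falls to 1 − s for an unknown share s. That relation assumes the same true event rate in both periods and complete recording in the main study within its own rules. The documents do not show that any events have been or will be lost, only that the text permits it and that the loss would be invisible in the eCRF.

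**What to change.** Reconcile the two paragraphs of Appendix K 2.4:

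- State that AEs and SAEs occurring after substudy consent are recorded in the eCRF whatever product is suspected.
- State that those thought related to another product are, in addition, reported to the manufacturer or authority as local rules require.
- Define spontaneous reports as those arising outside the substudy's AE collection, so that the term no longer overlaps with Section 6.3.5.

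If data have already been collected under the present text, the substudy SAP should either state that AE incidence is not compared with the main study, or apply the same event definition to both sides.

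The change concerns data recording only and leaves patient treatment untouched. It costs a short amendment and slightly more eCRF entry; the fallback costs SAP wording alone.
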